9.3.3. Secondary Endpoints

Endpoint	Statistical Analysis Methods		
Immunogenicity	For the first secondary immunogenicity estimand described in Section 3 for Cohort 2 + Cohort 3 combined:		
	• GMR of the SARS-CoV-2 reference-strain-neutralizing titer at 1 month after the study vaccination and the associated 2-sided 95% CIs will be calculated using the method described in Section 9.3.1.3 in participants with and without evidence of SARS-CoV-2 infection. A linear regression model that includes terms for baseline neutralizing titer and comparison group will be used to calculate the GMR and 95% CI, along with the model-based LS GMTs and associated 2-sided 95% CIs for each comparison group.		
	• Noninferiority will be established if the model-based lower bound of the 2-sided 95% CI for the GMR is greater than 0.67 and the point estimate of the GMR is ≥0.8.		
	Cohort 2/Group 2 + Cohort 3/Group 1 combined and Cohort 2/Group 4 + Cohort 3/Group 2 combined: At baseline and 1 month after the study vaccination:		
	• GMTs of SARS-CoV-2 Omicron (sublineages BA.4/BA.5)— neutralizing and reference-strain—neutralizing titers and 2-sided 95% CIs will be provided for each age group at each time point. GMTs will be summarized in participants with and without evidence of SARS-CoV-2 infection. Statistical methods are described in Section 9.3.1.3.		
	• GMFRs of SARS-CoV-2 Omicron (sublineages BA.4/BA.5)— neutralizing and reference-strain—neutralizing titers from baseline (before the study vaccination) to 1 month after the study vaccination, along with the associated 2-sided 95% CIs, will be provided for each age group. GMFRs will be summarized in participants with and without evidence of SARS-CoV-2 infection. Statistical methods are described in Section 9.3.1.4.		

Endpoint	Statistical Analysis Methods			
	 The percentages of participants with seroresponse to Omicron (sublineages BA.4/BA.5)— and reference-strain—neutralizing titers at 1 month after the study vaccination and the associated Clopper-Pearson 95% CIs will be provided for each age group. The percentages of participants with seroresponse will be summarized in participants with and without evidence of SARS-CoV-2 infection. GMTs, GMFRs, and percentages of participants with seroresponse, along with the associated 95% CIs, will also be summarized by baseline SARS-CoV-2 infection status. 			

9.3.4. Exploratory Endpoints

Endpoint	Statistical Analysis Methods	
Immunogenicity	Cohort 1: At baseline and 7 days, 1 month, 3 months, and 6 months after the study vaccination:	
	• GMTs and GMFRs of SARS-CoV-2 Omicron (sublineages BA.1 and BA.2)—neutralizing and reference-strain—neutralizing titers, and percentages of participants with seroresponse to SARS-CoV-2 Omicron (sublineages BA.1 and BA.2) and reference strain, along with the associated 95% CIs, will be summarized in the same way as described above for the primary immunogenicity endpoints of Cohort 1.	
	Cohort 2/Group 1, Cohort 2/Group 2 + Cohort 3/Group 1 combined Cohort 2/Group 4 + Cohort 3/Group 2 combined, Cohort 2/Group and Cohort 2/Group 5: At baseline and 1 month, 3 months, and 6 months after the study vaccination:	
	• GMTs and GMFRs of SARS-CoV-2 Omicron (sublineages BA.4/BA.5)-neutralizing and reference-strain-neutralizing titers, and percentages of participants with seroresponse to SARS-CoV-2 Omicron (sublineages BA.4/BA.5) and reference strain, along with the associated 95% CIs, will be summarized in the same way as described above for the primary immunogenicity endpoints of Cohort 1.	

Endpoint	Statistical Analysis Methods		
	Cohort 4: At baseline and 7 days, 1 month, 3 months, and 6 months after the study vaccination:		
	• GMTs and GMFRs of SARS-CoV-2 Omicron (sublineages BA.4/BA.5)-neutralizing and reference-strain-neutralizing titers, and percentages of participants with seroresponse to SARS-CoV-2 Omicron (sublineages BA.4/BA.5) and reference strain, along with the associated 95% CIs, will be summarized in the same way as described above for the primary immunogenicity endpoints of Cohort 4.		
COVID-19 cases	Cohort 1, Cohort 2 + Cohort 3 combined, and Cohort 4:		
	Confirmed COVID-19 cases, confirmed severe COVID-19 cases, and strain sequencing of the COVID-19 cases will be summarized for each vaccine and age group.		
Immune	Cohort 1, Cohort 2 + Cohort 3 combined, and Cohort 4:		
response to SARS-CoV-2 infection	• SARS-CoV-2-neutralizing titers at the time of a COVID-19 illness visit* and at the convalescent visit will be listed.		
imeedian	(*Only for in-person COVID-19 visits.)		
Immune	Cohort 1, Cohort 2 + Cohort 3 combined, and Cohort 4:		
response to other emerging variants (under monitoring, of interest, and/or of concern)	• GMTs of SARS-CoV-2 variant-neutralizing titers for other variants (under monitoring, of interest, and/or of concern) not already specified, along with the associated 2-sided 95% CIs, will be provided at specific time points for each vaccine group. GMFRs from baseline (before the study vaccination) to each subsequent time point, and percentage of participants with seroresponse at each time point after vaccination, along with the associated 2-sided 95% CIs, may also be provided for each vaccine group.		
Cell-mediated immune response	Cohort 2:		
	The cell-mediated immune response and additional humoral immune response parameters to the reference strain and Omicron variant will be summarized at each time point for the subset of participants with PBMC samples collected in each group.		

9.4. Interim Analyses

As C4591044 is a sponsor open-label, Phase 1/2/3 study, Pfizer may conduct unblinded reviews of the data during the course of the study for the purpose of safety assessment and/or supporting clinical development.

No formal interim analysis will be conducted. Statistical analyses will be carried out when the final data for specified objectives are available while the study is ongoing. The timing of these planned analysis and reporting events is described in Section 9.4.1.

9.4.1. Analysis Timing

Statistical analyses will be carried out when the following data are available for each of Cohort 1, Cohort 2, Cohort 2 + Cohort 3 combined, and Cohort 4:

- Safety and immunogenicity data through Visit 3 (1 month after study vaccination).
- Safety and immunogenicity data through Visit 5 (6 months after study vaccination).

Additional analyses may be conducted if required for regulatory purposes, to inform product development, and/or for program-level decisions. Certain analyses may be combined as 1 regulatory submission report if the data become available around the same time.

9.5. Sample Size Determination

Cohort 1, Cohort 2, and Cohort 4: For the immunogenicity analyses conducted separately for Cohorts 1, 2, and 4, the sample size is not based on any formal hypothesis test. All statistical analyses will be descriptive.

For safety outcomes, Table 8 shows the probability of observing at least 1 AE for a given true event rate of a particular AE. For example, if the true AE rate is 2%, with 60, 100, 200, or 300 participants in a group, there is 70%, 87%, 98%, and >99% probability of observing at least 1 AE, respectively.

Table 8. Probability of Observing at Least 1 AE by Assumed True Event Rate

Assumed True Event	N=60	N=100	N=200	N=300
Rate of an AE				
0.1%	0.06	0.10	0.18	0.26
0.3%	0.16	0.26	0.45	0.59
0.5%	0.26	0.39	0.63	0.78
0.8%	0.38	0.55	0.80	0.91
1%	0.45	0.63	0.87	0.95
2%	0.70	0.87	0.98	>0.99
3%	0.84	0.95	>0.99	>0.99
4%	0.91	0.98	>0.99	>0.99
5%	0.95	0.99	>0.99	>0.99

Cohort 2 + Cohort 3 combined: To provide sufficient power for the immunogenicity hypotheses for each of the age groups, the Cohort 2 18- through 55-year age and >55-year age groups receiving a 30-µg dose of BNT162b2 Bivalent (WT/OMI BA.4/BA.5) will be combined with the corresponding age and dose groups in Cohort 3.

Superiority and Noninferiority of Anti-Omicron Immunogenicity Objective

• For the >55-year age group (Cohort 2/Group 4 + Cohort 3/Group 2 combined vs BNT162b2 30-μg group from C4591031 Substudy E):

Assuming a 20% nonevaluable rate, with 300 participants >55 years of age receiving BNT162b2 Bivalent (WT/OMI BA.4/BA.5) 30 µg (100 in Cohort 2/Group 2 and 200 in Cohort 3/Group 2) and 300 participants >55 years of age receiving BNT162b2 30 µg (from C4591031 Substudy E), approximately 480 evaluable participants (240 in the BNT162b2 Bivalent (WT/OMI BA.4/BA.5) 30-µg group and 240 in the BNT162b2 30-µg group) will contribute to the immunogenicity evaluation. The superiority evaluation based on GMR and noninferiority evaluation based on seroresponse rate difference will each be performed at 1-sided alpha level of 0.025 as described in Section 9.1.2.

For comparisons based on GMR, common assay standard deviations at 1 month after the third or fourth dose in log scale is assumed to be 1.45 based on data observed in the C4591031 Substudy E. If the true GMR of Omicron–neutralizing titer in the BNT162b2 Bivalent (WT/OMI BA.4/BA.5) 30-µg group to the BNT162b2 30-µg group is 1.5, then 480 evaluable participants will provide 86.4% power to declare noninferiority.

For comparisons based on seroresponse rate difference, if the seroresponse rate is 65% in the BNT162b2 Bivalent (WT/OMI BA.4/BA.5) 30-µg group and 52% in the BNT162b2 30-µg group, the study has 98.0% power to demonstrate noninferiority using a 5% margin.

• For the 18- through 55-year age group (Cohort 2/Group 2 + Cohort 3/Group 1 combined) vs >55-year age group (Cohort 2/Group 4 + Cohort 3/Group 2 combined):

Assuming a 20% nonevaluable rate, with 300 participants receiving BNT162b2 Bivalent (WT/OMI BA.4/BA.5) 30 µg in the 18- through 55-year age group (100 in Cohort 2/Group 2 and 200 in Cohort 3/Group 1) and 300 participants receiving BNT162b2 Bivalent (WT/OMI BA.4/BA.5) 30 µg in the >55-year age group (100 in Cohort 2/Group 4 and 200 in Cohort 3/Group 2), approximately 240 evaluable participants in each age group (18- through 55-year age group and >55-year age group) will contribute to the immunogenicity evaluation. The noninferiority evaluation based on GMR and seroresponse rate difference will each be performed at 1-sided alpha level of 0.025 as described in Section 9.1.2.

For comparisons based on GMR, common assay standard deviations at 1 month after the third or fourth dose in log scale is assumed to be 1.45 based on data observed in the C4591031 Substudy E. If the true GMR of Omicron–neutralizing titer after BNT162b2 Bivalent (WT/OMI BA.4/BA.5) 30 µg in the 18- through 55-year age group to the >55-year age group is 1, then 480 evaluable participants (240 in the 18- through 55-year age group and 240 in the >55-year age group) will provide 86.4% power to declare noninferiority.

For comparisons based on seroresponse rate difference, if the seroresponse rate after BNT162b2 Bivalent (WT/OMI BA.4/BA.5) 30 μ g is 65% in the 18- through 55-year age group and 65% in the >55-year age group, the study has 63.4% power to demonstrate noninferiority using a 10% margin.

Noninferiority of Anti-Reference-Strain Immunogenicity Objective

For comparisons based on GMR, common assay standard deviations at 1 month after the third or fourth dose in log scale is assumed to be 1.05 based on data observed in the C4591031 Substudy E. If the true GMR of reference-strain–neutralizing titer after BNT162b2 Bivalent (WT/OMI BA.4/BA.5) 30 µg to after BNT162b2 30 µg in the >55-year age group is 1, then 480 evaluable participants (240 in the BNT162b2 Bivalent [WT/OMI BA.4/BA.5] 30-µg group and 240 in the BNT162b2 30-µg group) will provide 98.8% power to declare noninferiority using a 1.5-fold margin.

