Noninferiority based on GMR will be declared if the lower limit of the 2-sided 95% CI for the GMR is greater than 0.67; noninferiority based on seroresponse will be declared if the lower limit of the 2-sided 95% CI for the difference in percentages of participants with seroresponse is >-10%.

Noninferiority of Anti-Reference-Strain Immune Responses

The secondary immunogenicity objective is to assess the noninferiority of the anti-reference-strain immune response induced by BNT162b2 Bivalent (WT/OMI BA.4/BA.5) 30 µg in the >55-year age group relative to the anti-reference-strain immune response elicited by BNT162b2 30 µg in the >55-year age groups. The noninferiority objective will be evaluated by the following hypothesis:

• The null hypothesis (H₀) is

$$H_0: \ln(\mu_1) - \ln(\mu_2) \le \ln(0.67) \text{ vs } H_1: \ln(\mu_1) - \ln(\mu_2) > \ln(0.67)$$

where ln(0.67) corresponds to a 1.5-fold margin for noninferiority and

- Ln(μ₁) is the natural log of the geometric mean of SARS-CoV-2 reference-strain-neutralizing titers measured at 1 month after BNT162b2 Bivalent (WT/OMI BA.4/BA.5) 30 μg in the >55-year age group (Cohort 2/Group 4 + Cohort 3/Group 2);
- o Ln(μ_2) is the natural log of the geometric mean of SARS-CoV-2 reference-strain-neutralizing titers measured at 1 month after BNT162b2 in the >55-year age group from C4591031 Substudy E.

Noninferiority based on the GMR will be declared if the lower limit of the 2-sided 95% CI for the GMR is greater than 0.67 (1.5-fold criterion) and the point estimate of the GMR is \geq 0.8.

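### Two noninferiority powers in Protocol 9.5 (86.4% and 98.8%) match a margin of exactly 1/1.5; at the 0.67 used in the decision rules, the same calculation gives 85.5% and 98.6%.

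*Protocol*

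**What the plan says.** Protocol 9.1 sets the null hypothesis for both noninferiority comparisons of geometric mean ratios (GMRs) at ln(0.67) and describes that value as a 1.5-fold margin. For the 18- through 55-year group against the over-55 group the rule is: "Noninferiority based on GMR will be declared if the lower limit of the 2-sided 95% CI for the GMR is greater than 0.67". The reference-strain rule uses the same limit and adds that the estimated ratio must be at least 0.8. SAP 5.1.1 repeats both rules.

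Protocol 9.5 then gives the power.

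- **Age-group comparison:** the inputs are "approximately 240 evaluable participants in each age group", a true ratio of 1, and an SD described as "common assay standard deviations at 1 month after the third or fourth dose in log scale is assumed to be 1.45". The result is that 480 evaluable participants, "240 in the 18- through 55-year age group and 240 in the >55-year age group) will provide 86.4% power to declare noninferiority". This sentence names no margin.
- **Reference strain:** the inputs are 240 per group, a true ratio of 1, and an SD that "in log scale is assumed to be 1.05 based on data observed in the C4591031 Substudy E". The result is that the trial "will provide 98.8% power to declare noninferiority using a 1.5-fold margin".

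**The concern.** The number 0.67 is 1/1.5 rounded up to two decimals, so it is a slightly stricter bar than an exact 1.5-fold margin. If the power was computed at 1/1.5 while the test is judged at 0.67, the printed power belongs to a marginally easier test than the one the trial applies. Both noninferiority comparisons stand in the fixed testing sequence of Protocol 9.1.2, and 9.5 prints power to one decimal of a percentage point. At that precision the choice between 0.6667 and 0.67 shows. What is at stake is the accuracy of two planning figures, both of which err on the favourable side.

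**Working it through.** **Inputs, all from Protocol 9.5 and 9.1**

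- n = 240 evaluable per group (300 less 20%)
- 1-sided alpha 0.025, judged by the lower limit of a 2-sided 95% CI
- true GMR = 1
- log-scale SD: 1.45 (Omicron BA.4/BA.5), 1.05 (reference strain)
- margin M: 1/1.5 or 0.67

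**Formulas**

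SE = SD × √(2/240). Distance from the margin d = −ln(M). Noncentrality = d/SE. Power = P(T > 1.965), where T is noncentral t with 478 degrees of freedom and 1.965 is the 97.5% point of the central t.

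- SE at SD 1.45: 1.45 × √(2/240) = 0.1324
- SE at SD 1.05: 1.05 × √(2/240) = 0.0959
- d at 1/1.5: ln(1.5) = 0.4055
- d at 0.67: −ln(0.67) = 0.4005

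**Results**

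| Comparison | Margin | d/SE | Power (t) | Power (normal approx.) | Printed |
|---|---|---|---|---|---|
| 18–55 vs >55, SD 1.45 | 1/1.5 | 3.063 | 86.37% | 86.50% | 86.4% |
| 18–55 vs >55, SD 1.45 | 0.67 | 3.026 | 85.53% | 85.67% | – |
| Reference strain, SD 1.05 | 1/1.5 | 4.230 | 98.81% | 98.84% | 98.8% |
| Reference strain, SD 1.05 | 0.67 | 4.178 | 98.64% | 98.67% | – |

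The t results at 1/1.5 round to both printed figures. Neither method at 0.67 does. The gaps are 86.37 − 85.53 = 0.84 and 98.81 − 98.64 = 0.17 points.

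**How firmly the 1/1.5 margin is established.** For the reference strain, 9.5 states 1.5-fold itself. For the age-group comparison it is inferred from the match. A second sign supports the inference: 9.5 also prints 86.4% for the over-55 comparison with historical BNT162b2 at a true ratio of 1.5. That test is against a ratio of 1, so its distance is ln(1.5), and it reproduces at 86.37%. Two tests with the same n and SD share a power when their distances are equal, and they are equal here if the noninferiority margin is 1/1.5.

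**Does the 0.8 condition change the reference-strain figure?** No. At SD 1.05, a lower limit above 0.67 needs an observed ratio of at least 0.67 × exp(1.965 × 0.0959) ≈ 0.81. The 0.8 condition is then already met.

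**Sample size equivalent.** Restoring the printed powers at 0.67 would take about 246 evaluable per group for the age-group comparison and 245 for the reference strain (normal approximation), against 240 planned.

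**The case against.** The strongest reply is that this is rounding and that the documents say so: they define 1.5-fold as the label for 0.67, and every decision rule is written with 0.67. That stands. A reader might infer that the trial has two competing thresholds, so that a lower limit between 0.6667 and 0.67 would leave the result in dispute. The documents do not support this. Such a limit fails under every written rule, and no decision rule uses 0.6667. The 98.8% is also correct for the 1.5-fold margin that its own sentence names.

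A second reply is that 85.5% and 98.6% are not the power of the planned analysis either. The primary GMR comes from a regression that adjusts for baseline titer (Protocol 9.3.1.3, SAP 5.2.4), whereas 9.5 uses a plain two-sample calculation. The documents give no correlation between baseline and 1-month titer, so this can only be shown over an assumed range. If 1.45 is the unadjusted SD, the adjusted SD is about 1.45 × √(1 − r²). Power at 0.67 is then 85.9% for r = 0.1, 86.3% for r = 0.15, 86.9% for r = 0.2 and 88.6% for r = 0.3. So a reader should not take 85.5% and 98.6% as the true power of the primary analysis. They are what 9.5's own method gives at the margin the trial uses.

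Third, the gap is small against the inputs. Rounding of the SD alone (1.445 to 1.455) moves the power at 0.67 between 85.8% and 85.3%. The 18- through 55-year objective also needs the seroresponse test, for which 9.5 states 63.4% power, and joint power cannot exceed that. Both facts confirm that the point is minor. They do not make the printed figures match the stated rule.

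**Conclusion.** The point holds as a minor misstatement of power. The 86.4% and 98.8% correspond to a margin of exactly 1/1.5, explicitly for the reference strain and by inference for the age-group comparison. At the 0.67 in the decision rules, 9.5's assumptions give 85.5% and 98.6%, lower by about 0.8 and 0.2 points. This rests on 240 evaluable per group, SDs of 1.45 and 1.05, a true ratio of 1, and an unadjusted two-sample t calculation. The decision rule, the sample size, the 86.4% for superiority in the over-55 group and the trial's conclusions are unaffected.

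**What to change.** In Protocol 9.5:

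- Restate the power of the age-group GMR comparison as 85.5% and of the reference-strain comparison as 98.6%.
- Name 0.67 as the margin in both sentences. The first now names none, and the second says 1.5-fold.
- Add a short note that the calculation is an unadjusted two-sample one and does not use the baseline-titer adjustment of the primary analysis.

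Leave the decision rules at 0.67. The cost is a text correction that makes two figures slightly less favourable. Nothing changes in conduct, sample size or analysis.

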10. SUPPORTING DOCUMENTATION AND OPERATIONAL CONSIDERATIONS

10.1. Appendix 1: Regulatory, Ethical, and Study Oversight Considerations

10.1.1. Regulatory and Ethical Considerations

This study will be conducted in accordance with the protocol and with the following:

- Consensus ethical principles derived from international guidelines, including the Declaration of Helsinki and CIOMS International Ethical Guidelines;
- Applicable ICH GCP guidelines;
- Applicable laws and regulations, including applicable privacy laws.

The protocol, protocol amendments, ICD, SRSD(s), and other relevant documents (eg, advertisements) must be reviewed and approved by the sponsor, submitted to an IRB/EC by the investigator, and reviewed and approved by the IRB/EC before the study is initiated.

Any amendments to the protocol will require IRB/EC approval before implementation of changes made to the study design, except for changes necessary to eliminate an immediate hazard to study participants.

Protocols and any substantial amendments to the protocol will require health authority approval prior to initiation except for changes necessary to eliminate an immediate hazard to study participants.

The investigator will be responsible for the following:

- Providing written summaries of the status of the study to the IRB/EC annually or more frequently in accordance with the requirements, policies, and procedures established by the IRB/EC;
- Notifying the IRB/EC of SAEs or other significant safety findings as required by IRB/EC procedures;
- Providing oversight of the conduct of the study at the site and adherence to requirements of 21 CFR, ICH GCP guidelines, the IRB/EC, European regulation 536/2014 for clinical studies, European MDR 2017/745 for clinical device research, and all other applicable local regulations.

10.1.1.1. Reporting of Safety Issues and Serious Breaches of the Protocol or ICH GCP

In the event of any prohibition or restriction imposed (ie, clinical hold) by an applicable regulatory authority in any area of the world, or if the investigator is aware of any new information that might influence the evaluation of the benefits and risks of the study intervention, Pfizer should be informed immediately.

In addition, the investigator will inform Pfizer immediately of any urgent safety measures taken by the investigator to protect the study participants against any immediate hazard, and of any serious breaches of this protocol or of the ICH GCP guidelines that the investigator becomes aware of.

10.1.2. Financial Disclosure

Investigators and subinvestigators will provide Pfizer with sufficient, accurate financial information as requested to allow Pfizer to submit complete and accurate financial certification or disclosure statements to the appropriate regulatory authorities. Investigators are responsible for providing information on financial interests during the course of the study and for 1 year after completion of the study.

10.1.3. Informed Consent/Assent Process

The investigator or the investigator's representative will explain the nature of the study, including the risks and benefits, to the participant and/or his/her parent(s)/legal guardian and answer all questions regarding the study. The participant and/or his/her parent(s)/legal guardian should be given sufficient time and opportunity to ask questions and to decide whether or not to participate in the trial.

When consent is obtained from a participant's parent(s)/legal guardian, the participant's assent (affirmative agreement) must be subsequently obtained when the participant has the capacity to provide assent, as determined by the IRB/EC. If the investigator determines that a participant's decisional capacity is so limited, they cannot reasonably be consulted, then, as permitted by the IRB/EC and consistent with local regulatory and legal requirements, the participant's assent may be waived with source documentation of the reason assent was not obtained. If the study participant does not provide their own assent, the source documents must record why the participant did not provide assent (for example, the child is not of assenting age per local regulations or policies), how the investigator determined that the person signing the consent was the participant's parent(s)/legal guardian, the consent signer's relationship to the study participant, and that the participant's assent was obtained or waived. If assent is obtained verbally, it must be documented in the source documents.

If study participants are minors who reach the age of majority or if a child reaches the age of assent (per local IRB/EC requirements) during the study, as recognized under local law, the child or adolescent must then provide the appropriate assent or consent to document their willingness to continue in the study. For an adolescent who reaches the age of consent, parental consent would no longer be valid. If the enrollment of emancipated minors is permitted by the IRB/EC and local law, the participant must provide documentation of legal status to give consent without the permission of a legally authorized representative.

Participants must be informed that their participation is voluntary. Participants and/or the participant's parent(s)/legal guardian will be required to sign a statement of informed consent that meets the requirements of 21 CFR 50, local regulations, ICH guidelines, privacy and data protection requirements, where applicable, and the IRB/EC or study center.

The investigator must ensure that each participant and/or his/her parent(s)/legal guardian is fully informed about the nature and objectives of the study, the sharing of data related to the study, and possible risks associated with participation, including the risks associated with the processing of the participant's personal data.

The participant and/or his/her parent(s)/legal guardian must be informed that the participant's personal study-related data will be used by the sponsor in accordance with local data protection law. The level of disclosure must also be explained to the participant and/or his/her parent(s)/legal guardian.

The participant and/or his/her parent(s)/legal guardian must be informed that the participant's medical records may be examined by Clinical Quality Assurance auditors or other authorized personnel appointed by the sponsor, by appropriate IRB/EC members, and by inspectors from regulatory authorities.

The investigator further must ensure that each study participant and/or his/her parent(s)/legal guardian is fully informed about their right to access and correct the participant's personal data or their child's personal data and to withdraw consent for the processing of the participant's personal data or their child's personal data.

The source documentation must include a statement that written informed consent and as applicable, assent, was obtained before the participant was enrolled in the study and the date on which the written consent/assent was obtained. The authorized person obtaining the informed consent must also sign the ICD.

Participants and/or the participant's parent(s)/legal guardian must be reconsented to the most current version of the IRB/EC-approved ICD(s)/assent during their participation in the study as required per local regulations.

A copy of the ICD(s) and assent(s) must be provided to the participant and/or his/her parent(s)/legal guardian.

Participants who are rescreened are required to sign a new ICD.

